#### 7.6 Tumor Size

For all study parts, tumor size will be presented graphically using waterfall plots for each treatment arm, presenting each subject's Week 12 percentage change in tumor size as a separate bar with the bars ordered from the largest increase to the largest decrease. Reference lines at the +20% and -30% change in tumor size levels will be added to the plots, which correspond with the definitions of disease progression and PR, respectively. In these waterfall plots, the subjects whose Week 12 percentage change in tumor size is based on an imputation will be clearly identified. For Parts 1 and 2, the two treatment arms will be plotted separately, but presented side-by-side on a single page.

Waterfall plots of the best percentage change from baseline will also be presented, as described above for the Week 12 percentage change from baseline.

The percentage change from baseline in tumor size at Week 12 ( $\% \Delta TS_{Wk12}$ ) is a secondary endpoint for Part 1. In line with the exploratory objectives of the trial, the

statistical analysis of tumor size in Part 1 will be also be used to help evaluate the role of HER family expression levels as predictors of benefit to varlitinib. If a relationship is found between biomarker(s) expression and clinical outcomes in Part 1 of the study, the biomarker(s) could be prospectively evaluated in Part 2 of the study.

These analyses will be exploratory, and may be driven by the data observed, and specifically the prevalence of the HER family sub-groups of interest. However, the analysis principles to be followed are outlined below.

1. ASLAN will create and document a list of the key biomarkers of interest, based upon the biological plausibility of predictivity for clinical outcomes. The list will be limited to those biomarkers, or combinations of biomarkers for which a scientific hypothesis exists. These will represent the biomarkers that will be used to assess the listed exploratory objectives, providing that there is sufficient prevalence of that biomarker in the trial population.
2. For each biomarker of interest, each subject's baseline biomarker status will be independently evaluated blinded to study treatment and clinical outcome
3. For each biomarker sub-group, or combination of biomarkers identified on the prospectively defined list (step 1), if at least 15 subjects in the EFR population are determined to be expressors, then the role of that biomarker as a predictor of clinical outcome (tumor size) will be evaluated as described below.

For each biomarker of interest (or combination of biomarkers), the absolute values at baseline and Week 12, along with the percentage change from baseline target lesion size at Week 12 will be summarized using descriptive statistics and presented by treatment arm and baseline biomarker status.

The number and percentage of subjects in each treatment arm whose Week 12 data is imputed will also be presented (split by biomarker sub-group).

The effect of varlitinib on percentage change in tumor size will be estimated from an analysis of covariance (ANCOVA) model fitting the Week 12 percentage change from baseline as the response variable, and treatment, geographical location (US/Non-US), primary tumor location (GB/Non-GB), baseline biomarker status (positive or negative), the interaction treatment x baseline biomarker status, baseline tumor size, and the time from the baseline scan to randomization as covariates.

The significance of the interaction term will be evaluated at the one-sided 10% level, to determine whether there is evidence of a treatment biomarker interaction. Regardless of the significance of the interaction term, the number of subjects, unadjusted mean and adjusted least squares (LS) means for each treatment arm will be presented for each level of biomarker status factor (positive or negative), together with the difference in adjusted LS means between treatment arms for each level of the biomarker status factor, and corresponding p-value and 80% and 95% confidence intervals for the difference.

If the interaction term is not significant at the one-sided 10% level, the number of subjects, unadjusted mean and adjusted least squares (LS) means for each treatment arm will also be presented together with the difference in adjusted LS means between treatment arms and corresponding p-value and 80% and 95% confidence intervals for the difference.

If, at blind review, it is judged the data do not adequately follow a normal distribution assumption, then a log-transformation may be used. Specifically, in place of percent change in Week 12 value the ANCOVA model will use  $\log_e(\text{Week 12}/\text{baseline})$ . In this situation the ratio of the geometric LS means corresponding confidence interval and p-value will be presented.

As a sensitivity analysis a nonparametric analysis will be performed. The p-value from the ANCOVA model will be presented together with the Hodges Lehmann estimate of the median difference and corresponding 80% confidence interval which will be derived. The median percentage change and range will be presented for each treatment arm, together with the number of subjects and percentage of subjects in each treatment arm whose Week 12 data is imputed in the nonparametric analysis.

For all biomarkers of interest (step 1), waterfall plots color-coded by baseline biomarker status will be produced.

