If, at blind review, it is judged that the data do not adequately follow a normal distribution assumption, then a log-transformation may be used. Specifically in place of percent change in Week 12 value the ANCOVA model will use \log_e (Week 12/baseline). In this situation, the ratio of the geometric LS means corresponding CI and p-value will be presented.

As a sensitivity analysis, a nonparametric analysis will be performed. The Hodges Lehmann estimate of the median difference and corresponding 80% CI will be derived and presented. The median percentage change and range will be presented for each

treatment arm, together with the number of patients and percentage of patients in each treatment arm whose Week 12 data is imputed in the nonparametric analysis.

For all biomarkers of interest (step 1), waterfall plots color-coded by baseline biomarker status will be produced.

Note, due to the differing timeframes of the endpoints being available for analysis, the above statistical analyses of the biomarker data will be reported outside of the study CSR.

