### 3. ENDPOINTS

#### 3.1 Efficacy Endpoints

##### 3.1.1 Objective Response Rate

Objective Response Rate is a co-primary endpoint in Part 1 and a secondary endpoint in Part 2, and the Safety lead-in cohort.

ORR rate is defined as the number (%) of subjects with at least one visit response of CR or PR. Data obtained up until progression, or last evaluable assessment in the absence of progression, will be included in the assessment of ORR. This will be irrespective of whether or not subjects discontinued treatment or received a subsequent therapy prior to progression.

In all study parts, the primary assessment of ORR will be based on the full analysis set (FAS). Sensitivity analysis populations are described in Section 4.

The ORR is derived programmatically from the Best overall RECIST Response (BoR) for each subject.

Best overall RECIST Response (BoR) is calculated based on the overall visit responses from each RECIST assessment. It is the best response a subject has had following randomization and prior to RECIST progression or the last evaluable assessment in the absence of RECIST progression.

Categorization of BoR will be based on the RECIST criteria using the following response categories (listed in hierarchical order): complete response (CR), partial response (PR), stable disease (SD), progressive disease (PD) and inevaluable (NE) (CR>PR>SD>PD>NE).

Target Lesions (TL)	Non-Target Lesions (NTL)	New Lesions	Overall Response
CR	CR	NO	CR
CR	Non-CR/Non- PD	NO	PR
CR	Not evaluated	NO	PR
PR	Non- PD or not all evaluated	NO	PR

Target Lesions (TL)	Non-Target Lesions (NTL)	New Lesions	Overall Response
SD	Non- PD or not all evaluated	NO	SD
Not all evaluated	Non- PD	NO	NE
PD	ANY	YES or NO	PD
ANY	PD	YES or NO	PD
ANY	ANY	YES	PD

For the evaluation of the co-primary endpoint ORR in Part 1 of the study, all radiological data will be assessed by an Independent Central Review (ICR), and the BoR will be determined programmatically using the data provided by the ICR. For Part 2, the Safety lead-in and for the Part 1 secondary endpoint, ORR based on site assessments, BoR will be determined programmatically using data from the site assessments

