### 3.1.6 Tumor Size

The percentage change from baseline in tumor size at Week 12 ( $\% \Delta TS_{Wk12}$ ) is a secondary endpoint for Part 1, and will be used to present waterfall plots of the target lesion data in the Evaluable for Response (EFR) set (see Section 4.3), and also to help evaluate the exploratory objectives of investigating the possible role of HER family expression levels as predictors of clinical benefit. Tumor size is not considered to be a key secondary endpoint; for the purpose of marketing authorization, no statistical claims will be made based on tumor size.

The  $\% \Delta TS_{Wk12}$  will be defined as follows:

- Baseline tumor size (TS): defined as the sum of longest diameters of target lesions at baseline
- Week 12 TS: defined as the sum of longest diameters of target lesions at week 12

$$\% \Delta TS_{Wk12} = 100 \times \frac{Week\ 12\ TS - Baseline\ TS}{Baseline\ TS}$$

An increase from baseline of 20% will be imputed for any subjects who die by any cause, or withdraw from the study due to symptomatic disease progression prior to Week 12 (+5 days). Any subjects who withdraw from the study due to radiological disease progression prior to Week 12 will be included in the analysis, and will be assigned a percentage change from baseline of 20%, or the value that was observed at the time of disease progression (whichever is larger).

The best percentage change from baseline in tumor size ( $\% \Delta TS_{best}$ ) at any time point, will also be calculated and presented using waterfall plots.

The  $\% \Delta TS_{best}$  will be defined as follows:

- Baseline tumor size (TS): defined as the sum of longest diameters of target lesions at baseline
- Best TS: defined as the smallest sum of longest diameters of target lesions as observed at any time point post-randomization up until disease progression (regardless of whether it was a scheduled assessment).

$$\% \Delta TS_{best} = 100 \times \frac{Best\ TS - Baseline\ TS}{Baseline\ TS}$$

Subjects in the EFR set without any evaluable post-randomization target lesion data will be excluded from the waterfall plot of  $\% \Delta TS_{best}$ , except if the subject is known to have died or withdrawn from the study due to symptomatic disease progression prior to Week 12 (+ 5 days), or if non-target lesion or new lesion data is available prior to week 12 (+5 days) which is indicative of disease progression. In such cases, the subject will have an increase from baseline of 20% imputed.

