### 6.3 Handling of Dropouts or Missing Data

In general, missing data will remain missing and will not be included in analyses. Exceptions are described below.

- **Missing Baseline Data**

If a baseline (Day 1) value is not available and a screening value is available for the same parameter, then the last screening value will be used as baseline. This value will also be used for calculations of changes from baseline.

- **Missing % Change from Baseline in Sum of Longest Diameters of Target Lesions (TLs) at Week 12**

An increase from baseline of 20% will be imputed for any subjects who die by any cause, or withdraw from the study due to symptomatic disease progression prior to Week 12+ 5 days. Any subjects who withdraw from the study due to radiological disease progression prior to Week 12 will be included in the analysis, and will be assigned a percentage change from baseline of 20%, or the value that was observed at the time of disease progression (whichever is larger).

- **Missing Best % Change from Baseline in Sum of Longest Diameters of TLs at any time**

For the waterfall plot of the best % change from baseline, subjects with measurable disease at baseline (see Section 4.3), for whom no post-baseline TL data are available, will have an increase from baseline of 20% imputed in the following circumstances:

- The subject has died prior to week 12 (+ 5 days)
- Progression has been detected based on NTLs or new lesions prior to week 12 (+ 5 days)
- Subject has withdrawn due to symptomatic progression prior to week 12 (+ 5 days)

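### The optional log fallback for Week 12 tumour size has no value for a target-lesion sum of 0, so patients whose target lesions have all disappeared would leave that model (minor)

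*SAP*

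**What the plan says.** The planned analysis of Week 12 tumour size is an ANCOVA on percent change from baseline. Its terms are treatment, biomarker status, their interaction, and baseline covariates (SAP 7.6; protocol 8.5.2.1). If normality is doubted at blind review, "then a log-transformation may be used". SAP 7.6 continues: "Specifically, in place of percent change in Week 12 value the ANCOVA model will use" the natural log of Week 12 over baseline. The protocol's wording matches: "Specifically in place of percent change in Week 12 value the ANCOVA model will use" the same ratio.

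SAP 3.1.6 defines the numerator: "Week 12 TS: defined as the sum of longest diameters of target lesions at week 12". The response table in SAP 3.1.1 includes complete response of the target lesions, so a sum of 0 is a foreseeable value.

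SAP 6.3 sets the default: "In general, missing data will remain missing and will not be included in analyses", apart from listed exceptions. For Week 12 tumour size the exceptions cover only bad outcomes. "An increase from baseline of 20% will be imputed for any subjects who die by any cause", and likewise for withdrawal with symptomatic progression before Week 12. Withdrawal for radiological progression takes +20% or the observed value, whichever is larger.

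A nonparametric sensitivity analysis is planned. In SAP 7.6 the Hodges-Lehmann estimate is shown beside the p-value from the ANCOVA; the protocol gives the estimate and its interval without naming a p-value.

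**The concern.** Percent change keeps a patient with no measurable target lesion left, at -100%. The log ratio cannot. With no floor, offset or imputation for that case, following the written rules removes the patients with the greatest shrinkage and retains those with the worst outcomes. The loss is therefore one-sided.

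Three results are exposed if the fallback is used: the estimated treatment effect, the treatment-by-biomarker interaction tested at the one-sided 10% level, and the ANCOVA p-value that the SAP places beside the Hodges-Lehmann estimate. The interaction matters because the plan uses it to help judge biomarkers that could be evaluated prospectively in Part 2. It may be run with as few as 15 expressors, where one lost patient counts for more.

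Elsewhere the plan guards against a similar loss. In the ECG analysis (SAP 7.11.4.2, step 2), changes from baseline are tested both untransformed and log-transformed so that zero changes are not discarded. The tumour-size fallback has no such safeguard.

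**Working it through.** The plan gives no figure on this point, so there is none to reproduce.

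**1. Values at the extremes.** Let B be the baseline sum.
- Sum of 0 at Week 12: percent change = 100 × (0 - B)/B = -100. Log ratio = ln(0/B) = minus infinity, which is not a usable response.
- Imputed +20%: ln(1.2) = +0.182, retained.
- A 30% decrease: ln(0.7) = -0.357, retained.

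Only a sum of exactly 0 is lost. Partial shrinkage is unaffected.

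**2. How many patients.** The documents give 60 per arm and planning response rates of 10% and 30% (SAP 6.1.2). They do not give the share s of responders with a zero sum, so s = 5% to 30% is an assumption. It also treats best response as a stand-in for status at Week 12.
- Varlitinib: 60 × 0.30 × s = 0.9 to 5.4 patients.
- Control: 60 × 0.10 × s = 0.3 to 1.8 patients.
- Chance of at least one zero sum overall: 1 - (1 - 0.30s)^60 × (1 - 0.10s)^60 = 70% at s = 5% and over 99% at s = 30%.

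**3. Effect on the estimate.** Illustrative simulation with 60 per arm and 2000 runs. Assumed inputs: median baseline sum 70 mm (log SD 0.5); mean log ratio +0.05 on control and -0.10 on varlitinib, SD 0.3. The smallest varlitinib ratios were set to 0, with no zero sums on control. The model held treatment and baseline size only.

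| Zero sums on varlitinib | Percent-change difference, everyone kept (points) | Geometric mean ratio, zero sums dropped |
|---|---|---|
| 0 | -15.6 | 0.86 |
| 1 | -16.2 | 0.87 |
| 2 | -16.7 | 0.88 |
| 3 | -17.7 | 0.89 |

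The two scales move in opposite directions. Percent change shows a larger benefit as complete shrinkage is added; the log model shows a smaller one.

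**4. Sensitivity to a patch.** With 3 zero sums on varlitinib, adding a constant to both sums gives a ratio of 0.79 (5 mm), 0.72 (1 mm) or 0.64 (0.1 mm). Choosing the constant after seeing results would amount to choosing the estimate.

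**5. The interaction.** Write it as (V+ - P+) - (V- - P-), where each term is a mean log ratio by arm (V varlitinib, P placebo) and biomarker status. Losing a zero-sum patient raises that cell's mean. A loss from V+ pushes the interaction upward, hiding a biomarker-positive benefit. A loss from V- pushes it downward, exaggerating one. Losses on placebo reverse these signs. No single direction follows from the documents.

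**The case against.** The case for leaving this alone is substantial, and most of it limits the point without removing it.

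- **The fallback is optional.** It depends on a judgement at blind review, when pooled values of -100% would be visible before the log is chosen. This stands. But nothing tells the reviewers what to do with those values.
- **Only an exact zero is affected.** Protocol Appendix 14.1 adds the short axis of nodal lesions to the sum, so a sum that includes nodes need not reach 0. This stands and reduces the counts in step 2.
- **The endpoint carries little weight.** Tumour size is not a key secondary endpoint, no marketing claim rests on it, and the biomarker models are exploratory. This stands and sets the severity.
- **Other displays keep these patients.** Percent-change summaries, waterfall plots and the Hodges-Lehmann estimate can all include -100%. This stands, except that the SAP's accompanying p-value comes from the ANCOVA and would carry the exclusion under the fallback.

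A reader might infer more than the documents support. They do not say zero-sum patients are excluded; that follows from an undefined value and the SAP 6.3 default. They do not say strong responses would trigger the switch; the +20% imputations are another possible source of non-normality. Nor is tumour size the sole route to a Part 2 biomarker: it helps the evaluation, and ORR and PFS subgroup analyses by HER status are also planned.

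**Conclusion.** The gap is real and present in both documents, and it is minor. If the log fallback is used, the rules as written lose patients with a zero target-lesion sum and retain deaths and progressions at ln(1.2) or above. Shrinkage is then understated in whichever arm has more such patients. It would go too far to conclude that varlitinib's effect or the biomarker interaction will be biased towards no benefit: the first depends on where the zero sums fall by arm, the second on arm and biomarker group together.

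In the illustration the geometric mean ratio moves from 0.86 with no zero sums to between 0.87 and 0.89 when 1 to 3 varlitinib patients are dropped. The percent-change difference that keeps them strengthens from -15.6 to between -16.2 and -17.7 points. These sizes rest on assumed zero-sum counts, effect and variability. The undefined log and the absence of a rule for it do not.

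**What to change.** Amend SAP 7.6 and protocol 8.5.2.1 together.

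- **Preferred.** Where normality fails, fit the same ANCOVA (treatment, biomarker status, their interaction and the covariates already listed) to the ranks of Week 12 percent change. This keeps -100% and the imputed values in order and preserves the interaction test and covariate adjustment. Making the Hodges-Lehmann analysis the main one instead would lose both.
- **In either case.** Report the Hodges-Lehmann estimate with a rank-based p-value rather than the ANCOVA p-value.
- **If the log model is kept.** Before unblinding, fix one positive floor for a sum of 0. Keep in the model every patient in the evaluable-for-response set with an observed or imputed Week 12 value. Show a second floor as sensitivity, because the estimate depends on the choice.

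The cost is a few sentences in each document. The rank model gives no geometric mean ratio, and its interaction is on the rank scale, so the unadjusted percent-change summaries should stay beside it.

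### The SAP prints the ANCOVA p-value in the nonparametric sensitivity analysis of Week 12 tumour size and specifies no rank-based p-value; the protocol does not attach it

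*SAP*

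**What the plan says.** SAP 7.6 estimates the treatment effect on Week 12 percentage change in target lesion size by ANCOVA and reports differences in adjusted means with "corresponding p-value and 80% and 95% confidence intervals for the difference". The treatment-by-biomarker interaction has its own criterion: "The significance of the interaction term will be evaluated at the one-sided 10% level".

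The SAP then adds a check: "As a sensitivity analysis a nonparametric analysis will be performed". Its content is: "The p-value from the ANCOVA model will be presented together with the Hodges Lehmann estimate of the median difference", with the "corresponding 80% confidence interval which will be derived". The next sentence adds descriptive output: "The median percentage change and range will be presented for each treatment arm", along with how many values were imputed. No rank test is named and no 95% interval is planned for this analysis.

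Protocol 8.5.2.1 describes the same sensitivity analysis without any p-value: "The Hodges Lehmann estimate of the median difference and corresponding 80% CI will be derived and presented". SAP section 8, which records changes to the planned analysis, does not mention the difference.

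The outcome contains imputed values. SAP 3.1.6 states: "An increase from baseline of 20% will be imputed for any subjects who die by any cause". The same value applies to withdrawal for symptomatic progression before Week 12. Patients who withdraw for radiological progression before then receive 20% or their observed change, whichever is larger.

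**The concern.** The usual Hodges-Lehmann interval is obtained by inverting the Wilcoxon rank-sum test, so the p-value that belongs beside it is that of the rank-sum test. The SAP prints instead the p-value of the covariate-adjusted parametric model that the analysis is meant to check. That number is already in the ANCOVA table and carries no new information. A reader may take it for the p-value of the Hodges-Lehmann estimate, and it may contradict the interval next to it.

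It is also not clear which p-value is meant. The ANCOVA yields one for the interaction, one for the treatment difference at each biomarker level and, if the interaction is not significant, a pooled one. SAP 10.1 lists nonparametric tables both overall (14.2.6.4) and by subgroup (14.2.6.9), so a programmer would have to choose.

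The practical stake is the reading of exploratory biomarker results, which may influence which biomarkers are evaluated prospectively in Part 2.

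**Working it through.** The documents give no power or error figure for this analysis, so there is none to reproduce. The check compares the texts and then asks whether the outputs can conflict.

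**1. The two texts**

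| Element of the nonparametric analysis | Protocol 8.5.2.1 | SAP 7.6 |
|---|---|---|
| Hodges-Lehmann estimate | yes | yes |
| 80% interval | yes | yes |
| 95% interval | no | no |
| Rank-based p-value | no | no |
| ANCOVA p-value | no | yes |

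**2. What the interval tests.** With m and n patients per arm, the estimate is the median of the mn pairwise differences. In the normal approximation the limits are the c-th smallest and c-th largest differences, where c = floor(mn/2 − z·√(mn(m+n+1)/12)) and z = 1.2816 for 80%. An 80% interval that excludes zero is a rank-sum test at two-sided 20%, that is, 10% in each direction.

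**3. A constructed example** (10 per arm; a t-test stands in for the ANCOVA).
- Active: −35, −30, −28, −25, −22, −20, −18, −15, −12, 160. Mean −45/10 = −4.5.
- Control: −10, −8, −5, −2, 0, 3, 5, 8, 12, 20. Mean 23/10 = 2.3.
- Parametric: difference −6.8, t = −0.36 on 18 df, p = 0.72.
- Rank-sum: the active value exceeds the control value in 10 of 100 pairs (50 expected). SD = √(100 × 21/12) = 13.23; z = (10 − 50 + 0.5)/13.23 = −2.99; p = 0.003.
- Interval: c = floor(50 − 1.2816 × 13.23) = 33. Hodges-Lehmann estimate −23, 80% interval −28 to −17.

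Following the SAP wording, the table would show −23 (−28 to −17) with p = 0.72.

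**4. How often the outputs conflict.** There were 2,000 simulated trials per scenario, comparing ANCOVA p < 0.20 with the 80% interval excluding zero. From the documents: 60 per arm, and at least 15 biomarker expressors, taken as about 8 per arm. Assumed: SD 25 points; true effect 0 or −8 points; 0% or 30% of values set to +20% at the same rate in both arms; with or without 6% extreme outliers; ANCOVA reduced to treatment and baseline size.

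| 60 per arm | ANCOVA p < 0.20 | Interval excludes 0 | Conclusions differ |
|---|---|---|---|
| Effect 0 | 19.2% | 19.4% | 6.4% |
| Effect 0, outliers | 20.9% | 18.5% | 17.6% |
| Effect −8 | 67.1% | 64.6% | 7.8% |
| Effect −8, outliers | 42.2% | 62.8% | 29.0% |
| Effect 0, 30% imputed | 19.6% | 3.8% | 15.9% |
| Effect 0, 30% imputed, outliers | 21.1% | 3.6% | 18.6% |
| Effect −8, 30% imputed | 52.3% | 17.0% | 35.3% |
| Effect −8, 30% imputed, outliers | 36.0% | 16.0% | 25.8% |

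At 8 per arm the conclusions differed in 10% to 16% of trials.

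The first four rows are the cleaner evidence. In the last four, about 18 × 18 = 324 of 3,600 pairwise differences (9%) are exactly zero, and the interval becomes conservative: with no effect it excludes zero in under 4% of trials against a nominal 20%. Part of the disagreement in those rows is therefore tie handling.

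**The case against.** The strongest reply is that the check works without a rank-based p-value. The estimate and 80% interval are rank-based, the SAP requires them, and they can contradict the ANCOVA, as the example shows. The interval's level, one-sided 10%, is the level SAP 7.6 uses for the interaction and SAP 6.5.1 uses for Part 1 secondary efficacy endpoints. This stands. A reader might infer that the sensitivity analysis cannot disagree with the parametric result, or that it contains no independent test. The documents do not support either reading; only the printed p-value is unable to disagree.

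A second reply is that the ANCOVA p-value may be shown beside the Hodges-Lehmann result simply for comparison. That is possible, but the SAP does not say so and does not identify which ANCOVA p-value it means. On this reading the fault is one of labelling.

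A third reply is that non-normality is handled elsewhere: a log transformation may be chosen at blind review, imputed values are counted by arm, and imputed bars are marked in the waterfall plots. This helps, although a log transformation leaves tied values tied.

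**Conclusion.** The point holds in a narrow form. The SAP attaches to the nonparametric analysis a p-value from a different test, contrary to the protocol's description. That p-value adds no check on the ANCOVA and can conflict with the interval beside it. The rank-based check at the one-sided 10% level remains; what is missing is a rank-based p-value and any rank-based counterpart to the ANCOVA's 95% interval.

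The mismatch follows from the text alone. The simulated conflict rates depend on the assumed data and show only that conflict is not rare; they do not predict this trial.

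A reader might also infer from the planning assumptions that about half of the control values will be imputed. With exponential PFS and a median of 2.67 months, 1 − 0.5^(2.76/2.67) = 51% of controls have a PFS event by Week 12 (2.76 months). That is not the share set to +20%. Radiological progressors with larger growth keep their observed value, and progression found at the Week 12 scan comes with a real measurement. The 51% is at most a loose upper bound, and even that leaves aside withdrawals for symptomatic progression, which trigger imputation without being PFS events.

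Severity is low: both documents say that tumour size is not a key secondary endpoint and supports no statistical claims, and the biomarker use is exploratory.

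**What to change.** Amend the sentence in SAP 7.6:

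- Replace the ANCOVA p-value with that of the Wilcoxon rank-sum test that the Hodges-Lehmann interval inverts.
- Add the 95% interval to the 80% interval, so that both ANCOVA intervals have a counterpart.
- State how ties are handled, so that p-value and interval agree when several values equal +20%.
- If stratification by primary tumour location is wanted, use a stratified test such as van Elteren only with a matching stratified estimate and interval. Beside the standard unstratified interval it would recreate the mismatch.

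At minimum, delete the ANCOVA p-value so that the SAP agrees with Protocol 8.5.2.1.

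The cost is one SAP sentence, one procedure call and small edits to the shells of Tables 14.2.6.4 and 14.2.6.9. No new data are needed.
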